9.5 Analysis Populations

9.5.1 Immunogenicity Analysis Populations

The Per-Protocol (PP) population will serve as the primary population for the analysis of immunogenicity data in this study. The PP population consists of all randomized participants without deviations from the protocol that may substantially affect the results of the immunogenicity endpoint(s). Potential deviations that may result in the exclusion of a participant from the PP population for all immunogenicity analyses include:

- Failure to receive any study vaccine at Visit 1 (Day 1)
- Failure to receive correct clinical material as per randomization schedule at Visit 1 (Day 1) (ie, participants who were cross-treated)
- Receipt of prohibited medication or prohibited vaccine prior to study vaccination

Additional potential deviations that may result in the exclusion of a participant's measurement from a specific time point assessment in the PP population for immunogenicity analyses include:

- Receipt of prohibited medication or prohibited vaccine prior to a blood sample collection
- Collection of blood sample outside of the prespecified window (as described in Section 1.3)

The final determination on protocol deviations, and thereby the composition of the PP population, will be made prior to the final unblinding of the database. Participants will be included in the vaccination group to which they are randomized for the analysis of immunogenicity data using the PP population.

A supportive analysis using the Full Analysis Set (FAS) population will also be performed for the primary immunogenicity endpoints. The FAS population consists of all randomized participants who received at least 1 vaccination and have at least 1 serology result. Participants will be included in the vaccination group to which they are randomized for the analysis of immunogenicity data using the FAS population.

9.5.2 Safety Analysis Populations

Safety analyses will be conducted in the All Participants as Treated (APaT) population, which consists of all randomized participants who received study vaccination. Participants will be included in the group corresponding to the study vaccination they actually received for the analysis of safety data using the APaT population. This will be the group to which they are randomized except for participants who take incorrect study vaccination; such participants will be included in the treatment group corresponding to the study vaccination actually received.

At least 1 temperature measurement obtained subsequent to study intervention is required for inclusion in the analyses of temperature.

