7.3 Lost to Follow-up

If a participant fails to return to the clinic for a required study visit and/or if the site is unable to contact the participant, the following procedures are to be performed:

- The site must attempt to contact the participant and reschedule the missed visit. If the participant is contacted, the participant should be counseled on the importance of maintaining the protocol-specified visit schedule.
- The investigator or designee must make every effort to regain contact with the participant at each missed visit (eg, telephone calls and/or a certified letter to the participant's last known mailing address or locally equivalent methods). These contact attempts should be documented in the participant's medical record.
- Note: A participant is not considered lost to follow-up until the last scheduled visit for the individual participant. The missing data for the participant will be managed via the prespecified statistical data handling and analysis guidelines.

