8.1.9 Electronic Vaccination Report Card (eVRC)

The eVRC was developed to be administered electronically via a hand-held device. This item was structured as recommended in the final Food and Drug Administration Patient-Reported Outcome Guidance [U.S. Food and Drug Administration 2009]. The investigator or delegate will train the participant in the use of the eVRC at Visit 1 (Day 1).

Temperatures, injection-site reactions, vaccine-specific complaints, other complaints or illnesses, and concomitant medications or vaccinations will be recorded on the eVRC as

described in Section 1.3 and Section 8.3.4. The investigator or delegate will review the data captured on the eVRC with the participant at the Telephone Contact (Day 15) and Visit 2 (Day 30).

Any differences between eVRC data and the clinical database must be clearly explained in the participant's source documentation.

For the specific AEs collected via the eVRC, the investigator will use the information provided by the participant both on the eVRC and verbally at the time of eVRC review to apply the appropriate assessment of intensity and toxicity as described in Appendix 3.

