8.1.11 Discontinuation and Withdrawal

Participants who receive a single-dose intervention cannot discontinue study intervention (see Section 7.1).

When a participant withdraws from participation in the study, all applicable activities scheduled for the final study visit (Visit 2) should be performed (at the time of withdrawal). Any AEs that are present at the time of withdrawal should be followed in accordance with the safety requirements outlined in Section 8.4.

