Descriptive statistics with point estimates and within-group 95% CIs will be provided for all other immunogenicity endpoints. For the continuous endpoints, the point estimates will be calculated by exponentiating the estimates of the mean of the natural log values and the within-group CIs will be derived by exponentiating the bounds of the CIs of the mean of the natural log values based on the t-distribution. For the dichotomous endpoints, the within-group CIs will be calculated based on the exact method proposed by Clopper and Pearson [CLOPPER, C. J. and PEARSON, E. S. 1934].

Reverse Cumulative Distribution Curves for both OPA titers and IgG concentrations at 30 days postvaccination with each lot of V114 will be graphically displayed by serotype.

A detailed analysis strategy for immunogenicity endpoints is listed in [Table 4](#).

Table 4 Analysis Strategy for Immunogenicity Variables

Endpoint/Variable (Description, Time Point)	Primary vs. Supportive Approach [†]	Statistical Method [‡]	Analysis Population	Missing Data Approach
Primary Endpoint				
OPA GMTs at Day 30	P	cLDA [§] (estimate, 95% CI, p-values)	PP	Model-based
	S		FAS	
Secondary Endpoint				
IgG GMCs at Day 30	P	cLDA [§] (estimate, 95% CI)	PP	Model-based
GMFRs and proportions of participants with a ≥ 4 -fold rise from baseline to 30 days postvaccination for both OPA and IgG responses	P	Descriptive Statistics (estimate, 95% CI)	PP	Missing data will not be imputed
[†] P = Primary approach; S = Supportive approach. [‡] Statistical models are described in further detail below: [§] cLDA model with terms for vaccination group, time, the interaction of time-by-vaccination, age stratum at baseline, and age stratum-by-time interaction. CI = confidence interval; cLDA = constrained longitudinal data analysis; FAS = Full Analysis Set; GMC = Geometric Mean Concentration; GMFR = geometric mean fold rise; GMT = Geometric Mean Titer; IgG = Immunoglobulin G; OPA= opsonophagocytic activity; PP = Per-Protocol.				

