9.6.2 Statistical Methods for Safety Analyses

Safety and tolerability will be assessed by clinical review of all relevant parameters, including AEs and postvaccination temperature measurements.

Consistency of the safety profile across lots will be assessed via point estimates and 95% CIs (for select safety endpoints) within each of the V114 vaccination groups (Lot 1, Lot 2, Lot 3). Details will be provided in the sSAP. The analysis of safety will then be performed for V114 overall (combining the Lot 1, Lot 2, and Lot 3 vaccination groups) versus the Prevnar 13™ vaccination group following a tiered approach as detailed below (Table 5).

The tiers differ with respect to the analyses that will be performed. AEs (specific terms as well as system organ class [SOC] terms) are either pre-specified as “Tier 1” endpoints or will be classified as belonging to "Tier 2" or "Tier 3" based on the number of events observed.

Tier 1 Events

Safety parameters or AEs of special interest that are identified a priori constitute “Tier 1” safety endpoints that will be subject to inferential testing for statistical significance with p-values and 95% CIs to be provided for between-treatment differences in the proportion of participants with events; these analyses will be performed using the Miettinen and Nurminen (M&N) method [Miettinen, O. and Nurminen, M. 1985], an unconditional, asymptotic method. For this protocol, solicited injection-site AEs (redness/erythema, swelling, and tenderness/pain) from Day 1 through Day 5 postvaccination and solicited systemic AEs (muscle pain/myalgia, joint pain/arthralgia, headache, and tiredness/fatigue) from Day 1 through Day 14 postvaccination are considered Tier 1 events.

Tier 2 Events

Tier 2 parameters will be assessed via point estimates with 95% CIs provided for differences in the proportion of participants with events (also via the M&N method) [Miettinen, O. and Nurminen, M. 1985].

Membership in Tier 2 requires that at least 36 participants in the V114 combined group (combining Lot 1, Lot 2, and Lot 3 vaccination groups) or 4 participants in the Prevnar 13™ group exhibit the event. Because many 95% CIs for Tier 2 events may be provided without adjustment for multiplicity, the CIs should be regarded as a helpful descriptive measure to be used in review, not a formal method for assessing the statistical significance of the between-group differences in AEs.

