In addition, the broad AE categories consisting of the proportion of participants with any AE, a vaccine-related AE, an SAE, a vaccine-related SAE, and death will be considered Tier 2 endpoints. Nonserious adverse events (NSAEs) will be followed for 14 days postvaccination and SAEs will be followed for 6 months postvaccination. The proportion of participants with maximum temperature measurements meeting the Brighton Collaboration cut points will also be considered Tier 2 endpoints.

Tier 3 Events

Safety endpoints that are not Tier 1 or 2 events are considered Tier 3 events. Only point estimates by treatment group are provided for Tier 3 safety parameters.

Table 5 Analysis Strategy for Safety Parameters

Safety Tier	Safety Endpoint [†]	p-Value [‡]	95% CI for Between-Group Comparison [‡]	Descriptive Statistics
Tier 1	Injection-site redness/erythema (Days 1 to 5)	X	X	X
	Injection-site swelling (Days 1 to 5)	X	X	X
	Injection-site tenderness/pain (Days 1 to 5)	X	X	X
	Muscle pain/myalgia (Days 1 to 14)	X	X	X
	Joint pain/arthritis (Days 1 to 14)	X	X	X
	Headache (Days 1 to 14)	X	X	X
	Tiredness/fatigue (Days 1 to 14)	X	X	X
Tier 2	Any AE [†]		X	X
	Any Vaccine-Related AE [†]		X	X
	Any SAE [†]		X	X
	Any Vaccine-Related SAE [†]		X	X
	Death [†]		X	X
	Maximum temperature measurements meeting the Brighton Collaboration cut points (Days 1 to 5)		X	X
	Specific AEs by SOC and PT [§] (incidence ≥36 participants in the combined V114 group or ≥4 participants in the Prevnar 13 TM group)		X	X
Tier 3	Specific AEs by SOC and PT [§] (incidence <36 participants in the combined V114 group and <4 participants in the Prevnar 13 TM group)			X
[†] These endpoints are broad AE categories. For example, descriptive statistics for the safety endpoint of “Any AE” will provide the number and percentage of participants with at least 1 AE. [‡] These analyses will be performed using the M&N method [Miettinen, O. and Nurminen, M. 1985]. [§] Includes only those endpoints not prespecified as Tier 1 or not already prespecified as Tier 2 endpoints. AE = adverse event; CI = confidence interval; M&N = Miettinen and Nurminen; PT = preferred term; SAE = serious adverse event; SOC = system organ class; X = results will be provided.				

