9.6.3 Demographic and Baseline Characteristics and Other Analysis

The comparability of the vaccination groups for each relevant demographic and baseline characteristic will be assessed using summary tables. No statistical hypothesis tests will be performed on these characteristics. The number and percentage of participants randomized and discontinued from the study and discontinuation reasons will be displayed. Demographic variables (age, race, and gender), baseline characteristics, the number (%) of subjects reporting specific prior medications within 14 days prior to the first vaccination, the number (%) of subjects reporting specific concomitant medications within 14 days following any vaccination, the number (%) of subjects reporting specific prior vaccinations within 30 days prior to the first vaccination, and the number (%) of subjects reporting specific concomitant vaccinations within 30 days following any vaccination will be summarized by vaccination group either by descriptive statistics or categorical tables.

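### Does the plan leave open how vaccinated participants with no solicited-AE follow-up are counted in the Tier 1 proportions?

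*Combined protocol and SAP*

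**What the plan says.** Section 9.5.2 places safety analyses in APaT, "which consists of all randomized participants who received study vaccination", grouped by the vaccine actually received. The same section sets one data-availability condition: the temperature analyses need at least one post-vaccination reading. It sets no such condition for adverse events.

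Section 9.4.2 defines the solicited-AE endpoints as proportions of participants with the event, over Days 1 to 5 (injection site) or Days 1 to 14 (systemic). Section 9.6.2 makes these seven events Tier 1, "subject to inferential testing for statistical significance with p-values and 95% CIs", by the Miettinen and Nurminen method for combined V114 against Prevnar 13.

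On missing data, Section 7.3 states: "The missing data for the participant will be managed via the prespecified statistical data handling and analysis guidelines". In Section 9.6.1, Table 4 has a missing-data column for immunogenicity, with entries such as "Missing data will not be imputed". The safety counterpart, "Table 5 Analysis Strategy for Safety Parameters", has no such column.

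On follow-up, Section 8.1.9 has site staff "review the data captured on the eVRC with the participant at the Telephone Contact (Day 15) and Visit 2 (Day 30)". Section 8.1.11 says that on withdrawal "all applicable activities scheduled for the final study visit (Visit 2) should be performed (at the time of withdrawal)". Section 9.6.3 adds: "The number and percentage of participants randomized and discontinued from the study and discontinuation reasons will be displayed".

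**The concern.** Section 7.3 promises a prespecified rule, and Section 9.1 says that Sections 9.2 to 9.12 hold the comprehensive plan. A reader who looks there finds a missing-data entry for every immunogenicity endpoint and none for safety, even though the solicited AEs are primary endpoints and the only adverse events tested with p-values.

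Two treatments are conceivable for a vaccinated participant with no diary day entered and no diary review completed at Day 15, Day 30 or withdrawal. One keeps the participant in the denominator as a non-event; the other leaves the participant out. The first gives a lower rate if any unobserved participant had the event. The comparator has only 220 participants, so unequal loss could shift the between-group difference. A reader of the results also could not tell an observed non-event from an unknown one. At stake would be the stated reactogenicity rates and the V114 minus Prevnar 13 differences. The lot-equivalence hypothesis is not touched, because its missing data are handled by the model.

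**Working it through.** **What the text fixes**

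| Element | Source | Consequence |
|---|---|---|
| Denominator | Section 9.5.2: all vaccinated | Participant without follow-up stays in |
| Numerator | Section 9.4.2: participants with the event | No recorded event, so not in the numerator |
| Data requirement | Section 9.5.2: temperature only | None for solicited AEs |

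Read together, these give the non-event convention. An event noted at the 30-minute observation would still count as an event.

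**The plan's own safety figures**

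Section 9.9.2 assumes all 2000 V114 participants are evaluable.
- Chance of at least one SAE at 1 in 1243: 1 − (1 − 1/1243)^2000 = 0.800 (stated 80%).
- At 1 in 2885: 1 − (1 − 1/2885)^2000 = 0.500 (stated 50%).
- Upper bound with no events: 1 − 0.025^(1/2000) = 0.184%, about 1 in 542 (stated 0.18%).

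The Table 6 row used below, 39.3% versus 30.0% with 2000 and 220 participants, gives 78% power by the pooled two-proportion formula, in line with the stated approximate 80%.

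**How far the two treatments differ**

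Let m be the share without solicited-AE follow-up. The documents do not give it; 1% to 10% is assumed, equal in both groups and with equal underlying risk.

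- Counted as non-events: rates are 39.3(1 − m) and 30.0(1 − m), and the difference is 9.3(1 − m), with n = 2000 and 220.
- Excluded: rates and difference are unchanged, with n = 2000(1 − m) and 220(1 − m).
- Test statistic at a null difference of 0: z = (p1 − p2) / √[p̄(1 − p̄)(1/n1 + 1/n2)·N/(N − 1)], where p̄ is the pooled rate and N = n1 + n2.

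Full data: p̄ = (786 + 66)/2220 = 0.3838, z = 0.093/0.03455 = 2.69, p = 0.0071.

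| m | Rates as non-events | Difference (points) | p, non-event | p, excluded (difference 9.3) |
|---|---|---|---|---|
| 1% | 38.9% vs 29.7% | 9.2 | 0.0076 | 0.0074 |
| 5% | 37.3% vs 28.5% | 8.8 | 0.0098 | 0.0087 |
| 10% | 35.4% vs 27.0% | 8.4 | 0.0132 | 0.0107 |

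The 95% CI half-width with full data is 1.96·√(0.393·0.607/2000 + 0.30·0.70/220) = 6.4 points. The gap between treatments, 9.3m, is 0.1 to 0.9 points.

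**Unequal loss, same row (assumed)**

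| Loss V114 / Prevnar 13 | Difference, non-event | p | p, excluded (difference 9.3) |
|---|---|---|---|
| 5% / 2% | 7.9 | 0.020 | 0.008 |
| 10% / 5% | 6.9 | 0.042 | 0.009 |
| 2% / 5% | 10.0 | 0.004 | 0.009 |

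The gap reaches 2.4 points in the most extreme case, and none of these cases crosses 0.05.

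**The case for a change.** The strongest argument for a change is that membership of a population is not the same as event status. APaT says who is analysed; it does not say that an unobserved member is a non-event. The temperature sentence can be turned round as well: it shows the authors departing from the full denominator when data are absent, and temperature is collected on the same electronic diary. The places where Section 9 cites the supplemental SAP (non-convergence of the IgG model, within-lot safety, subgroups) do not cover this point. The unequal-loss cases show that the choice can move a p-value from 0.009 to 0.042.

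Some of this stands. The convention is inferred rather than written, and Table 5 does lack the entry that Table 4 has. The discontinuation display is also not quite the count one would want: someone who misses the Day 15 and Day 30 contacts but is reached at Month 6 would not appear in it.

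It does not carry the point further. A data requirement written for one safety measure, in the very section that defines the population, is most naturally read as not applying to the others. The unequal-loss examples rest on assumed imbalances in a double-blind trial with one injection, two scheduled diary reviews, Visit 2 procedures at withdrawal and repeated contact attempts. A sensitivity analysis restricted to people with at least one diary day would not separate observed from unknown non-events either, because blank days in a partly completed diary would still count as no event.

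**Conclusion.** No change to the plan is needed. This is a gap in wording that analysts fill sensibly: APaT denominator, recorded events in the numerator, non-event otherwise. Stating the rule would reproduce the analysis already planned, so nothing is gained in the primary safety results.

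If an analyst excluded these participants instead, equal loss of 1% to 10% would change the 9.3-point difference in the example by 0.1 to 0.9 points, well inside a half-width of 6.4 points, with no change in conclusion. This rests on assumed loss rates. The 90% evaluability figure in Section 9.9.1 is a planning allowance for immunogenicity, not a bound on loss of safety follow-up. It also rests on equal loss and equal risk in the two groups; the unequal-loss cases show larger shifts but no crossing of 0.05. The supplemental SAP is not among the documents and may already state the convention. A count by vaccination group of participants without solicited-AE follow-up would be a reasonable optional addition to the report, but the plan does not depend on it.

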9.6 Statistical Methods

Statistical testing and inference for immunogenicity and safety analyses are described in Section 9.6.1 and Section 9.6.2, respectively. Unless otherwise stated, all statistical tests will be conducted at the $\alpha=0.05$ (2-sided) level. Section 9.6.3 describes how demographic and baseline characteristics will be summarized.

9.6.1 Statistical Methods for Immunogenicity Analyses

This section describes the statistical methods that address the primary and secondary immunogenicity objectives.

Immunogenicity analyses will be conducted separately for each of the 15 pneumococcal serotypes across the 3 different lots of V114 (Lot 1, Lot 2, and Lot 3).

Primary Endpoint/Hypothesis

The primary objective (to compare the serotype-specific OPA GMTs at 30 days postvaccination [Day 30] across the 3 different lots of V114) will be assessed via the primary hypothesis.

Each possible pairwise comparison of lots will be made (Lot 1 to Lot 2, Lot 1 to Lot 3, and Lot 2 to Lot 3). Each possible pairwise comparison of lots will consist of two 1-sided tests at the $\alpha=0.025$ level. Rejecting the null hypothesis of nonequivalence for any test is equivalent to requiring the bounds of the 95% CI on the pairwise lot-to-lot comparison of the V114 GMT ratios to be between 0.5 and 2.0.

For each of the 15 serotypes in V114 and for each pairwise comparison, OPA GMTs between participants administered different lots of V114 at 30 days postvaccination will be compared via the following equivalence hypotheses:

H_0 : $\text{GMT}_x/\text{GMT}_y < 0.5$ or $\text{GMT}_x/\text{GMT}_y > 2.0$ versus

H_1 : $0.5 \leq \text{GMT}_x/\text{GMT}_y \leq 2.0$

where GMT_x is serotype-specific OPA GMT for one of the V114 lots and GMT_y is serotype-specific OPA GMT for another V114 lot. A ratio between 0.5 and 2.0 corresponds to ensuring that there's no more than a 2.0-fold difference between OPA GMTs across any of the V114 lots (Lot 1 vs Lot 2, Lot 1 vs Lot 3, and Lot 2 vs Lot 3). Rejecting the null hypothesis (H_0) at the two 1-sided $\alpha=0.025$ level corresponds to the bounds of the 95% CI on the GMT ratio between each V114 lot (Lot 1/Lot 2, Lot 1/Lot 3, and Lot 2/Lot 3) being between 0.5 and 2.0 and would lead to the conclusion that the OPA responses for the 15 serotypes across the V114 lot are equivalent.

Estimation of the GMT ratios and 95% CIs, and the hypothesis test will be conducted using a cLDA method proposed by Liang and Zeger [Liang, K-Y and Zeger, S. L. 2000] utilizing data from the participants randomized to V114. In this model, the response vector consists of the log-transformed antibody titers at baseline (Visit 1 [Day1]) and 30 days postvaccination (Visit 2 [Day 30]). The repeated-measures model will include terms for vaccination group (V114 Lot 1, V114 Lot 2, and V114 Lot 3), time, the interaction of time-by-vaccination group (with a restriction of the same baseline mean across groups), age stratum (ie, 50 to 64 years, 65 to 74 years, and ≥ 75 years) at baseline, and age stratum-by-time interaction. This model will allow for different baseline means for each stratum, but restrict the baseline mean within the age stratum levels to be the same for all V114 vaccination groups. An unstructured covariance matrix will be used to model the correlation among repeated measurements. The Kenward-Roger adjustment will be used with restricted (or residual) maximum likelihood to make proper statistical inference. This model allows the inclusion of participants who are missing either the baseline or postbaseline measurements, thereby increasing efficiency.

Secondary Endpoints

A similar statistical model as used for the primary objective will be used to address the secondary objective that evaluates the serotype-specific IgG GMCs at 30 days postvaccination compared across 3 different lots of V114 and combined lots of V114 compared to Prevnar 13™. Given the disparity in sample size across the intervention groups for the combined lots of V114 versus Prevnar 13™ comparison, convergence issues for the model are possible due to sensitivity of the model to differences in covariance structure between time points across intervention groups. Details of the methods to be used for this analysis if any of the models fail to converge will be provided in the sSAP.

Descriptive statistics with point estimates and within-group 95% CIs will be provided for all other immunogenicity endpoints. For the continuous endpoints, the point estimates will be calculated by exponentiating the estimates of the mean of the natural log values and the within-group CIs will be derived by exponentiating the bounds of the CIs of the mean of the natural log values based on the t-distribution. For the dichotomous endpoints, the within-group CIs will be calculated based on the exact method proposed by Clopper and Pearson [CLOPPER, C. J. and PEARSON, E. S. 1934].

Reverse Cumulative Distribution Curves for both OPA titers and IgG concentrations at 30 days postvaccination with each lot of V114 will be graphically displayed by serotype.

A detailed analysis strategy for immunogenicity endpoints is listed in [Table 4](#).

Table 4 Analysis Strategy for Immunogenicity Variables

Endpoint/Variable (Description, Time Point)	Primary vs. Supportive Approach [†]	Statistical Method [‡]	Analysis Population	Missing Data Approach
Primary Endpoint				
OPA GMTs at Day 30	P	cLDA [§] (estimate, 95% CI, p-values)	PP	Model-based
	S		FAS	
Secondary Endpoint				
IgG GMCs at Day 30	P	cLDA [§] (estimate, 95% CI)	PP	Model-based
GMFRs and proportions of participants with a ≥ 4 -fold rise from baseline to 30 days postvaccination for both OPA and IgG responses	P	Descriptive Statistics (estimate, 95% CI)	PP	Missing data will not be imputed
[†] P = Primary approach; S = Supportive approach. [‡] Statistical models are described in further detail below: [§] cLDA model with terms for vaccination group, time, the interaction of time-by-vaccination, age stratum at baseline, and age stratum-by-time interaction. CI = confidence interval; cLDA = constrained longitudinal data analysis; FAS = Full Analysis Set; GMC = Geometric Mean Concentration; GMFR = geometric mean fold rise; GMT = Geometric Mean Titer; IgG = Immunoglobulin G; OPA= opsonophagocytic activity; PP = Per-Protocol.				

